3. PEEP = 5 cmH₂O.
4. FiO₂ = .50.

4.1.2.3 Assessment for Tolerance

Patients will be assessed for tolerance using the following criteria:

1. Total respiratory rate < 35 (5 min at respiratory rate > 35 may be tolerated).
2. SpO₂ $\geq 88\%$ (< 15 min at $< 88\%$ may be tolerated).
3. No respiratory distress (two or more of the following):
 - (a) Heart rate greater than 120% of the 0600 rate (≤ 5 min at $>120\%$ may be tolerated).
 - (b) Marked use of accessory muscles.
 - (c) Abdominal paradox.
 - (d) Diaphoresis.
 - (e) Marked subjective dyspnea.

If any of goals 1, 2, or 3 are not met on initial set-up to PS, the ventilator mode will be changed back to A/C at most recent A/C settings and the patient will be reassessed the next morning.

4.1.2.4 Subsequent ventilator settings during weaning.

1. Reduce PS level by 5 cm H₂O q1-3 hours. PS will not be decreased below 5 cmH₂O. No decreases in PS will be made after 1900.
2. If PS = 10, 15 or 20 cmH₂O is not tolerated, then return to A/C (patient will remain in previously assigned study group at last A/C settings).
 - (a) At 0600-1000 of the next day, return to last PS level tolerated and continue with step 1.
3. If PS level = 5 cmH₂O is not tolerated, increase PS by 5 cmH₂O to 10 cmH₂O and maintain until the following morning.
 - (a) If a patient on PS=5 or10 must go back to A/C for reasons other than intolerance to weaning (e.g. surgical or other invasive procedures), the weaning sequence will be re-entered with section 4.1.2.1.
4. If PS = 5 cm H₂O is tolerated for two or more hours (using tolerance criteria 1-3 above), assess for ability to sustain unassisted breathing (section 4.1.2.5).

4.1.2.5 Assess for ability to sustain unassisted breathing.

A trial of spontaneous breathing will be initiated on CPAP (5 cm H₂O, T-piece, or tracheostomy mask with FiO₂ ≤ .50. The following criteria will be required to continue with spontaneous breathing:

1. SpO₂ ≥ 90% and/or PaO₂ ≥ 60 mmHg.
2. Spontaneous tidal volume ≥ 4 ml/kg ideal body weight.
3. Respiratory Rate ≤ 35/min.
4. pH ≥ 7.30 if measured.
5. No respiratory distress (2 or more of the following):
 - (a) Heart rate > 120% of the 0600 rate (≤ 5 min at ≥ 120% may be tolerated).
 - (b) Marked use of accessory muscles.

6. Abdominal paradox.
7. Diaphoresis.
8. Marked subjective dyspnea.

If criteria 1-5 are met for > 120 minutes, unassisted breathing will continue (step 4.1.2.6). If any of criteria 1-5 are not met during the 120 minute trial, then PS will resume at 5 cmH₂O and tolerance will be reassessed (step 4.1.2.3).

4.1.2.6 Definition of unassisted breathing.

1. Extubated with face mask, nasal prong oxygen, or room air, OR
2. T-tube breathing, OR
3. Tracheostomy mask breathing, OR
4. CPAP = 5 without PS or IMV assistance.

4.1.3 Completion of ventilator procedures.

Patients will be considered to have completed the study ventilator procedures if any of the following conditions occur:

1. Death.
2. Hospital discharge.
3. Alive 28 days after randomization.

If a patient requires positive pressure ventilation after a period of unassisted breathing, the study ventilator procedures for the group to which the patient was randomized will resume unless the patient was discharged from the hospital or > 28 days elapsed since enrollment.

4.1.4 Premature withdrawal from treatment

Patients will be removed from the protocol if they develop neurologic conditions for which hypercapnia would be contraindicated (Appendix A.#7).

5 Data Collection

5.1 Background Assessments

1. Demographic and Admission Data.
2. Pertinent Medical History and Physical Examination.
3. Height; calculated predicted body weight (PBW).
4. Time on ventilator prior to enrollment.
5. Type of Admission
 - (a) Scheduled surgical
 - (b) Medical
 - (c) Unscheduled surgical
6. Presence of following chronic diseases:
 - (a) Metastatic cancer (proven by surgery, computed tomographic scan, or other documented method).
 - (b) Hematologic malignancy (lymphoma, acute leukemia, or multiple myeloma).
 - (c) AIDS with complications (PCP pneumonia, Kaposi's sarcoma, lymphoma, tuberculosis, or toxoplasmosis).

5.2 Baseline Assessments

The following information will be recorded during the four-hour interval that precedes initial protocol ventilator changes (if any). Parameters indicated with "*" will be measured during the four-hour interval. If more

than one value is available during the four-hour interval, the last value will be recorded. For other parameters, most recent values will be recorded. If no values are available during the preceding 24 hours, then values will be measured during the four-hour interval prior to initial ventilator changes (if any).

1. * Vital Signs: heart rate (b/min), systolic and diastolic BP (mmHg), body temperature (°C), total respiratory rate.
2. *Ventilator Parameters: Mode, ventilator rate, tidal volume (inspired), FiO₂, PEEP, plateau pressure (0.5 second pause), ventilator manufacturer and model.
3. Measured body weight (kg).
4. Arterial PO₂, PCO₂, and pH and SpO₂.
5. Urinary output (most recent 24 hour value).
6. Serum electrolytes, BUN, creatinine and glucose.
7. Blood hematocrit, WBC, and platelets.
8. Serum albumin concentration.
9. * Blood for cytokines, mediators, and markers of lung injury. Plasma obtained from two, 10 ml EDTA anticoagulated blood samples will be divided immediately after centrifugation into 12 equal 1 ml aliquots in specified tubes and frozen at -70°C.
10. *Glasgow coma score.
11. Frontal chest radiograph (when available):
 - (a) Radiographic Lung Injury Score ([33], # of quadrants)
 - (b) Presence/absence of barotrauma:
 - i. pneumothoraces (R/L)
 - ii. pneumomediastinum
 - iii. pneumatocelles > 2 cm minimum diameter (R/L)
 - iv. subcutaneous emphysema
12. Administration of the following medications (Y/N):

- (a) Sedatives
- (b) Neuromuscular blocking agents
- (c) Vasopressors (maximum number given simultaneously)
- (d) Corticosteroids (dose ranges)
- (e) Buccal smear for genetic analysis in patients who have consented to genetic testing.

Most recent values for the following additional parameters will be recorded only if they are available from clinically required measurements.

13. Pulmonary artery systolic, diastolic, mean and pulmonary artery occlusion pressures, central venous pressure, and cardiac index.

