7. Increased intracranial pressure, tricyclic antidepressant overdose (if most recent blood level elevated or no blood level available), Hgb SS, Hgb SC, or other conditions where hypercapnia would be contraindicated.
8. Severe chronic respiratory disease.
9. Morbid obesity.
10. Burns $\geq 30\%$ total body surface area.
11. Malignancy or other irreversible disease or condition for which 6-month mortality is estimated $\geq 50\%$.
12. Bone marrow transplant.
13. Lung transplant.
14. Not committed to full support.
15. Severe chronic liver disease (Child-Pugh Score of 10 -15).
16. Vasculitis with diffuse alveolar hemorrhage.

- **Efficacy:** The primary efficacy variable is mortality prior to hospital discharge to 60 days.

Secondary efficacy variables include:

1. Ventilator Free Days, which is the number of days of unassisted breathing after initiating spontaneous breathing to day 28 after randomization (if at least 48 consecutive hours unassisted breathing were achieved). This efficacy measure is related to differences in mortality, morbidity, and cost attributable to differences in time to recovery from respiratory failure or time to death.
2. Percentage of patients who achieve 48 consecutive hours unassisted breathing prior to 28 days.
3. Number of ICU-free days from randomization to day 28.
4. Number of Organ Failure Free Days from randomization to day 28 (renal, hepatic, central nervous system, coagulation, circulation).
5. Number of days meeting commence-weaning criteria from randomization to day 28.
6. Number of days after initially achieving unassisted breathing from randomization to day 28.
7. Incidence of barotrauma (pneumothoraces, pneumatoceles > 2 cm largest diameter, pneumomediastinum).
8. Percentage of patients discharged alive from hospital.
9. Mortality and days of unassisted breathing for patients with pre- randomization $\text{PaO}_2/\text{FiO}_2 \leq 200$.

Part II

Study Description

Large Prospective, Randomized, Multi-Center Trial of Higher End-expiratory Lung Volume/Lower FiO₂ versus Lower End-expiratory Lung Volume/Higher FiO₂ Ventilation in Acute Lung Injury and Acute Respiratory Distress Syndrome

Protocol for the NIH NHLBI ARDS Network July 20, 1999

1 Background

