- 4 Number of Organ Failure Free days at 28 days after randomization, using previously validated definitions for renal, central nervous, coagulation, circulation, and hepatic organ and system failures [35], [36].
- 5 Number of days between the day of first meeting criteria to commence-weaning and day 28 after randomization.
- 6 Number of days between the day of initially achieving unassisted ventilation and day 28 after enrollment.
- 7 Incidence of barotrauma (pneumothoraces, pneumatoceles > 2 cm largest diameter, pneumomediastinum).
- 8 Percentage of patients discharged alive from hospital. Patients alive in hospital at 60 days will be considered to have been discharged alive.
- 9 Mortality and days of unassisted breathing with pre-randomization $\text{PaO}_2/\text{FiO}_2 \leq 200$.

3 Study Population and Enrollment

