5.3 Assessments During Enrollment

The following data will provide the basis for assessing protocol compliance and safety as well as between-group differences in several efficacy variables. Data for each of the variables will be recorded on the days shown in the Time-Events schedule (Appendix C) or until death, discharge from intensive care unit, or unassisted ventilation for 48 hours.

Reference Measurements

The following parameters will be measured and recorded between 0600 and 1000 on the days specified in the Time-Events schedule (Appendix C). The following conditions will be ensured prior to measurements: supine position for 15 minutes; no endobronchial suctioning for 10 minutes; no invasive procedures or ventilator changes for 30 minutes. SpO₂ sensors will be checked for optimal position, cleanliness, and consistent readings with satisfactory waveforms, if displayed. SpO₂ values will be observed for 1 minute and a representative value recorded. All vascular pressures will be zero-referenced to the mid-axillary line.

1. If receiving positive pressure ventilation:
 - (a) Ventilator mode
 - (b) Ventilator set inspired tidal volume (if on volume cycled mode)

- (c) Pressure Support level (if on PS for weaning)
 - (d) Total respiratory rate
 - (e) Total minute ventilation
 - (f) PEEP
 - (g) Plateau pressure (if on volume cycled mode)
 - (h) Peak inspiratory pressure (if on volume cycled mode)
2. FiO₂
 3. SpO₂ on current FiO₂
 4. Hemodynamic values
 - (a) Arterial systolic, diastolic and mean pressures
 - (b) Heart Rate (beats/min)

Values for the following variables will be recorded for the dates shown in the Time-Events Schedule. If the measurements are not obtained during the 4-hour reference interval, then the value obtained closest in time to the reference interval on the respective date will be recorded. If more than one value is obtained during the reference interval, then the earliest value during the interval will be recorded.

5. Weight (kg), using same technique for each measurement (bed-scale vs lift vs other)
6. Blood hemoglobin concentration
7. Arterial PO₂, PCO₂, and pH and calculated bicarbonate concentrations
8. Requirements for the following medications (Y/N):
 - (a) Sedatives and tranquilizers
 - (b) Neuromuscular blocking agents
 - (c) Vasopressors (maximum number given simultaneously)
 - (d) Experimental treatments: nitric oxide, fluorocarbons, surfactants, extracorporeal gas exchange (ECMO, ECCO2R, etc.)

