9. AP frontal chest radiograph

- (a) Presence/absence of barotrauma (as described for baseline assessments)
 - (b) Radiographic Lung Injury Score ([33], number of quadrants)
10. “Brussels Score” data:
- (a) Worst PaO₂/FiO₂ ratio for the date
 - (b) Worst systolic blood pressure for the date
 - (c) Worst creatinine, bilirubin, and platelet count for the date
 - (d) Use of a vasopressor (Y/N)
 - (e) Glasgow Coma Score
11. Blood for cytokines, mediators, and markers of lung injury.

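### The pneumatocele size criterion differs between the barotrauma outcome (largest diameter) and the data-collection list (minimum diameter), so barotrauma would be slightly under-counted if the list is followed literally

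*Supplement*

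**What the plan says.** The outcome is stated twice with the same criterion. Secondary variable 7 in the Study Summary reads "Incidence of barotrauma (pneumothoraces, pneumatoceles > 2 cm largest diameter, pneumomediastinum", and Section 2 (End-Points), item 7, repeats "pneumatoceles > 2 cm largest diameter, pneumomediastinum".

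The data behind it are specified elsewhere. Section 5.2 (Baseline Assessments), item 11(b), lists the barotrauma findings to be marked present or absent on the frontal film. The third is "pneumatocelles > 2 cm minimum diameter (R/L"; the fourth, "subcutaneous emphysema", is not part of the outcome. Section 5.3 (Assessments During Enrollment), item 9(a), then asks for "Presence/absence of barotrauma (as described for baseline assessments". The Section 5.3 data are meant to support safety assessment and "between-group differences in several efficacy variables".

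Section 5.4 (Endpoint Determinations) has no separate barotrauma item. The amendments of October 1999, January 2000, May 2000 and October 2000 leave all of these passages unchanged.

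**The concern.** The outcome and the recording rule name different dimensions of the same lesion. Section 5.2 governs a baseline film, but the cross-reference in Section 5.3 carries its wording to the post-randomization films from which the outcome is built.

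The item is a presence/absence mark by side, and no diameter is listed for recording. If a site applies the wording literally, a lesion that meets the outcome definition but not the recording rule is entered as absent, and the listed data give no way to find it later.

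Adverse event reporting is not a dependable backstop. Section 7.2 records experiences that are both clinically important and unexpected, whereas Sections 1.1 and 1.2.2 already name barotrauma as a risk of higher PEEP. Appendix B has adverse events reported in the case report form but gives no size rule for pneumatoceles.

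At stake is the count for a safety-relevant secondary outcome in a trial that compares higher with lower PEEP.

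**Working it through.** The plan states no figure for this outcome, so there is none to reproduce. The check is a comparison of texts followed by an illustrative range.

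**1. Outcome against recording list**

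| Finding | Outcome 7 (Study Summary; Section 2) | Recorded (Section 5.2, carried into 5.3) |
|---|---|---|
| Pneumothorax | counted | recorded, by side |
| Pneumomediastinum | counted | recorded |
| Pneumatocele | largest diameter > 2 cm | minimum diameter > 2 cm, by side |
| Subcutaneous emphysema | not counted | recorded |

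Subcutaneous emphysema has its own line in the list, so an analyst can leave it out if the lines are kept separate. A lesion that was never marked cannot be put back in the same way.

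**2. Direction of the error**

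For any lesion, minimum diameter ≤ largest diameter. Hence minimum > 2 cm implies largest > 2 cm, but not the reverse. The literal rule produces no false positives against the outcome definition. It misses exactly the lesions with largest diameter > 2 cm and minimum diameter ≤ 2 cm, for example one of 3.0 x 1.5 cm.

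**3. Which patients are affected**

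A patient with a pneumothorax, a pneumomediastinum or a pneumatocele over 2 cm in both dimensions is still counted. A patient is misclassified only if the sole finding is a pneumatocele between the two thresholds.

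**4. Illustrative size**

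From the documents: a maximum of 750 patients, taken as 750 / 2 = 375 per arm. The remaining inputs are assumptions with no source in the documents:
- barotrauma by the outcome definition: 10% of patients;
- cases whose only finding is a pneumatocele: 5% to 20%;
- share of those lying between the two thresholds: 25% to 50%.

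Cases per arm: 375 x 0.10 = 37.5.

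Share of cases missed, f:
- low: 0.05 x 0.25 = 0.0125 (1.25%);
- high: 0.20 x 0.50 = 0.10 (10%).

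Patients missed per arm:
- low: 37.5 x 0.0125 = 0.47;
- high: 37.5 x 0.10 = 3.75.

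The share f does not depend on the assumed 10%; the number of patients does, in proportion.

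**5. Effect on the comparison**

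Let p1 and p0 be the true risks in the two arms, with the same share f missed in each.
- Risk ratio: p1(1 − f) / [p0(1 − f)] = p1 / p0, unchanged.
- Risk difference: (1 − f)(p1 − p0), which keeps 98.75% of its size at f = 0.0125 and 90% at f = 0.10.

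The documents do not show whether f would be equal between arms.

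**The case against.** The strongest reply is that the two texts may mean the same thing. The Section 5.2 wording could be a loose way of setting a size floor of about 2 cm. The line also misspells the lesion, so a deliberate second threshold cannot be presumed. This stands as a possibility, and the documents do not settle it. Against it, the greater-than sign already sets the floor, which leaves *minimum* with nothing to do on that reading; and the word sits where *largest* sits in the outcome definition. If both readings are open, film readers at about 24 hospitals may apply different rules, and no central or masked reading is described that would make them uniform.

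It is also fair to say that the case report form is not shown and that the content of the event schedule in Appendix C is not available. What sites were actually asked to mark is therefore unknown. The point concerns the protocol's list, and it applies only on the days that schedule names, up to the limits given in Section 5.3.

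A reader might infer three stronger things that the documents do not support:
- *That the barotrauma outcome cannot be built.* Pneumothorax and pneumomediastinum are listed as the outcome defines them, and part of the pneumatocele component is captured too.
- *That the main expected harm of the higher-PEEP arm is being hidden.* Section 1.1 names barotrauma beside circulatory depression, stretch injury, hypercapnia and acidosis without ranking them, and Section 8 (Risk Assessment) does not name it. The same recording rule applies in both arms, and equal under-recording leaves the risk ratio unchanged.
- *That a new rule is needed on whether findings already present at baseline count.* That is a separate question, and the diameter mismatch does not bear on it.

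**Conclusion.** The inconsistency is real and stands in the current text. Read literally, the recorded pneumatoceles are a subset of those secondary outcome 7 counts, so the outcome cannot be built exactly as defined, and any error is an under-count.

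The effect is probably small. The documents give no frequency or size distribution for pneumatoceles, so the range of 0.5 to 3.8 patients per arm shows scale only and is not an estimate. It assumes that sites follow the literal wording; if they read it as a simple 2 cm floor on the lesion's size, little or nothing is lost. The primary outcome, sample size and stopping rules are untouched. This is a minor correction, worth making because it is cheap and removes a contradiction from a safety-relevant outcome.

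**What to change.** In Section 5.2, item 11(b)iii, replace *minimum* with *largest*, so that the recorded item matches the outcome definition in the Study Summary and Section 2. Section 5.3, item 9(a), inherits the change through its cross-reference and needs no edit. The case report form should be checked for the same wording.

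The cost is one word in the protocol and, if needed, one on the form. Films already read under the literal wording would need a check for pneumatoceles near the threshold, because no recorded measurement would identify them.

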5.3 Assessments During Enrollment

The following data will provide the basis for assessing protocol compliance and safety as well as between-group differences in several efficacy variables. Data for each of the variables will be recorded on the days shown in the Time-Events schedule (Appendix C) or until death, discharge from intensive care unit, or unassisted ventilation for 48 hours.

Reference Measurements

The following parameters will be measured and recorded between 0600 and 1000 on the days specified in the Time-Events schedule (Appendix C). The following conditions will be ensured prior to measurements: supine position for 15 minutes; no endobronchial suctioning for 10 minutes; no invasive procedures or ventilator changes for 30 minutes. SpO₂ sensors will be checked for optimal position, cleanliness, and consistent readings with satisfactory waveforms, if displayed. SpO₂ values will be observed for 1 minute and a representative value recorded. All vascular pressures will be zero-referenced to the mid-axillary line.

1. If receiving positive pressure ventilation:
 - (a) Ventilator mode
 - (b) Ventilator set inspired tidal volume (if on volume cycled mode)

- (c) Pressure Support level (if on PS for weaning)
 - (d) Total respiratory rate
 - (e) Total minute ventilation
 - (f) PEEP
 - (g) Plateau pressure (if on volume cycled mode)
 - (h) Peak inspiratory pressure (if on volume cycled mode)
2. FiO₂
 3. SpO₂ on current FiO₂
 4. Hemodynamic values
 - (a) Arterial systolic, diastolic and mean pressures
 - (b) Heart Rate (beats/min)

Values for the following variables will be recorded for the dates shown in the Time-Events Schedule. If the measurements are not obtained during the 4-hour reference interval, then the value obtained closest in time to the reference interval on the respective date will be recorded. If more than one value is obtained during the reference interval, then the earliest value during the interval will be recorded.

5. Weight (kg), using same technique for each measurement (bed-scale vs lift vs other)
6. Blood hemoglobin concentration
7. Arterial PO₂, PCO₂, and pH and calculated bicarbonate concentrations
8. Requirements for the following medications (Y/N):
 - (a) Sedatives and tranquilizers
 - (b) Neuromuscular blocking agents
 - (c) Vasopressors (maximum number given simultaneously)
 - (d) Experimental treatments: nitric oxide, fluorocarbons, surfactants, extracorporeal gas exchange (ECMO, ECCO2R, etc.)
9. AP frontal chest radiograph

- (a) Presence/absence of barotrauma (as described for baseline assessments)
 - (b) Radiographic Lung Injury Score ([33], number of quadrants)
10. “Brussels Score” data:
- (a) Worst PaO₂/FiO₂ ratio for the date
 - (b) Worst systolic blood pressure for the date
 - (c) Worst creatinine, bilirubin, and platelet count for the date
 - (d) Use of a vasopressor (Y/N)
 - (e) Glasgow Coma Score
11. Blood for cytokines, mediators, and markers of lung injury.

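### Barotrauma is an incidence outcome, but the only radiograph rule described keeps one film per scheduled date, so transient events can go uncaptured

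*Supplement*

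**What the plan says.** Section 2, item 7 names the outcome: "Incidence of barotrauma (pneumothoraces, pneumatoceles > 2 cm largest diameter, pneumomediastinum"). It gives no source film, time window or derivation rule.

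Section 5.3 introduces its data as the basis for "assessing protocol compliance and safety as well as between-group differences in several efficacy variables". For items 5 to 11 it sets one sampling rule in three parts:

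- Dates: "Values for the following variables will be recorded for the dates shown in the Time-Events Schedule".
- No value in the 0600-1000 reference interval: "then the value obtained closest in time to the reference interval on the respective date will be recorded".
- Several values in the interval: "If more than one value is obtained during the reference interval, then the earliest value during the interval will be recorded".

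Item 9, the AP frontal chest radiograph, is in that list. Its part (a) is "Presence/absence of barotrauma (as described for baseline assessments"). Item 10, the Brussels data, is in the same list but carries its own instruction, for example "Worst systolic blood pressure for the date" and "Worst creatinine, bilirubin, and platelet count for the date".

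Section 5.4 (Endpoint Determinations) has no barotrauma item. No chest-tube item or item covering the time between films is described, and none of the amendments through October 2000 changes the radiograph item.

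**The concern.** Incidence means any new occurrence during follow-up. One selected film per scheduled date measures whether barotrauma is visible at that moment, which is closer to repeated point prevalence. The two agree when air persists until the next selected film. They part when an event appears and is treated between selected films, and an acute pneumothorax that is promptly drained can do that.

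Item 10 shows that the protocol departs from the default rule where it wants the day's worst finding. It does not do so for barotrauma. Sections 1.1 and 1.2.2 both name barotrauma as a risk of higher PEEP, which is the strategy under test, so this outcome bears on the balance of benefit and harm.

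**Working it through.** The documents state no barotrauma rate, sample size or power, so there is no plan figure to reproduce. The check is mainly textual.

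**Step 1. Apply the rule to possible film sequences.**

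| Films | Film the rule keeps | Item 9(a) |
|---|---|---|
| Scheduled date: 0700 clear, 1800 positive; cleared before next selected film | 0700 | Absent |
| Scheduled date: 0630 clear, 0930 positive; cleared before next selected film | 0630 (earliest) | Absent |
| Scheduled date: 0500 clear, 1800 positive, none in interval; cleared before next selected film | 0500 (1 h from interval, against 8 h) | Absent |
| Positive film on a date not in the schedule; cleared before next selected film | None that day | Absent |
| Scheduled date: 1800 positive is the only film | 1800 | Present |
| Positive on an unselected film and still visible on the next selected film | The later film | Present |

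The first four rows lose the event and the last two keep it.

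**Step 2. Look for another route.** Section 7.2 has investigators review adverse experiences daily, but puts on the form only those that are clinically important and unexpected. Appendix B says that all adverse events in the study period go on the case report form. It calls an event unexpected if the protocol does not identify it by type, severity or frequency. Barotrauma is identified by type in sections 1.1, 1.2.2 and 2, but no frequency or severity is given, and the risk list in section 8 does not name it. Sites could reasonably decide either way. Neither section feeds outcome 7.

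**Step 3. Size, by assumption only.** The content of Appendix C is not shown, so the gap G between selected films is unknown. If onset is uniform over the gap and an event stays visible for a time D, the captured share is c = min(1, D/G).

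- G = 24 h (daily films): D = 6 h gives 6/24 = 25%; 12 h gives 12/24 = 50%; 24 h or more gives 100%.
- G = 168 h (weekly films): D = 12 h gives 12/168 = 7%; 24 h gives 24/168 = 14%; 72 h gives 72/168 = 43%.

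**Step 4. Effect on the comparison.** If both arms have the same capture c, the observed rates are c·p1 and c·p2. The risk ratio c·p2/(c·p1) = p2/p1 is unchanged. The difference becomes c·(p2 − p1).

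Power = Φ[(d − 1.96·se0)/se1], where d is the observed difference, se0 uses the pooled rate and se1 the separate rates. I take n = 750/2 = 375 per arm and a two-sided 0.05 test. For assumed true rates of 5% and 10%:

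- c = 100%: (0.05 − 1.96 × 0.01924)/0.01915 = 0.64, power 74%.
- c = 50%: (0.025 − 1.96 × 0.01387)/0.01384 = −0.16, power 44%.

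| Assumed true rates | c = 100% | 90% | 75% | 50% |
|---|---|---|---|---|
| 5% vs 10% | 74% | 69% | 61% | 44% |
| 10% vs 15% | 54% | 50% | 42% | 29% |
| 10% vs 20% | 97% | 95% | 90% | 74% |

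**The case against.** The strongest reply is that the protocol never says outcome 7 comes only from the item 9 film, and no separate analysis plan is shown in which a derivation could stand. That is right. A reader might infer that item 9(a) is the sole source and that a drained pneumothorax is never counted; the documents do not support so firm a statement. An emergency film is itself recorded when the rule selects it, persistent air is seen later, and Appendix B offers a partial route through adverse events, with coordinators viewing patient records. What survives is narrower: an analysis plan cannot recover a film that the collection rule leaves off the form, and the adverse-event route is uncertain and unlinked.

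A reader might also infer that the safety tables seen by the DSMB are biased. No section describes DSMB tables built from these films; section 7.2 says the DSMB reviews adverse events. That inference should be dropped.

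On size, the objection is fully right. With daily films and events visible for at least 24 h, the formula above gives no loss. The Glasgow Coma Score days in Amendment 4 say nothing about films.

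Finally, a fixed film schedule has a real merit. Ventilator settings are visible to clinicians, who may order unscheduled films differently by arm. An any-film count is open to that, and the fix has to allow for it.

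**Conclusion.** The concern holds in limited form. A stated sampling rule, and not mere silence, can set aside a positive film for an outcome defined as incidence, and no other described item is tied to that outcome. Transient barotrauma between selected films may therefore be under-counted.

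If the loss is equal in the two arms, both incidences, the absolute difference and power fall, while the risk ratio stays about the same. No mechanism for unequal loss is shown, so a claim of bias in the relative comparison is not supported. The amount of loss is unknown: across the assumptions above, capture runs from 7% to 100%, and the power figures rest on assumed rates. The primary mortality endpoint is unaffected. This is worth correcting because barotrauma is a named risk of the tested strategy and the correction is cheap.

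**What to change.** 1. Exempt item 9(a) from the closest-to-interval and earliest-value rule. For each day of the collection period, record any new pneumothorax, pneumomediastinum or qualifying pneumatocele on any clinically obtained chest film or CT, and any chest tube placed for barotrauma, with date and side.
2. Define outcome 7 as the first new event after randomization, setting aside findings already present under baseline item 11(b) of section 5.2.
3. Keep the scheduled-film rule for the radiographic lung injury score, item 9(b).
4. Report barotrauma on scheduled films alone as a sensitivity analysis, to show whether differences in the ordering of unscheduled films could drive the result.

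The cost is one changed sentence, one form line abstracted from existing reports, and a little extra chart review. No extra films or readers are needed. The remaining downside is the possible ascertainment difference between arms, which step 4 makes visible but does not remove.
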